Participants are considered active in the study for six months, from the time that they enroll in the program to the completion of the six-month post-enrollment follow-up survey.

The target analytic sample size for the impact study is 768 participants, with study groups being equal in size, for a target of 384 in-person participants and 384 on-demand participants.

Participant eligibility criteria. Individuals are eligible to participate in the program if they are incarcerated adults aged 18 years or older and within nine months of release from prison. All program enrollees who are receiving services at a site that has been authorized by the Ohio Department of Rehabilitation and Corrections (ODRC) to use tablets (and so can offer both delivery formats) for this program are eligible for the impact evaluation after giving informed consent to be randomly assigned to a study group. Approvals are for a specific tablet that the state of Ohio has granted a contract to provide technology services and devices into prisons across the state. Each warden (head of the specific institution) must approve the program delivered via tablet in their specific institution. This design allows for more equal opportunity for participants to be assigned to either delivery format. It also puts less burden on The RIDGE Project to meet enrollment numbers at numerous locations in order to get a sufficient sample to randomize. Program participants who have other commitments that prevent them from being able to participate in the in-person workshops are not eligible for random assignment; these participants are still offered TYRO Couples programming, but they are not part of the impact study sample. This within-facility design offers The RIDGE Project the opportunity to serve those in need without ever having to deny eligible applicants. In instances where unexpected situations arise, such as technological issues with the tablets, participants can opt out of the treatment group and receive in person services if it is more convenient or preferable to them. This would remove the participant from the study, but still allow the participant to continue with the TYRO curriculum. Having sites offer both delivery formats is invaluable for program delivery.

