The unit of randomization for this study is the individual. Participants are randomly assigned to a study group using the last single digit of their inmate number, a six-digit identifier assigned by the facility based on an inmate's chronological intake order. Because it is assigned by the facility, program staff and researchers have no influence in deciding who ends up in each study group, leaving it completely at random. With this method, half of the inmate population bears an even number, and the other half bears an odd number. The inmate number remains with the participant, which can also be used to look up their incarceration status within the ODRC facilities. Within a given cohort, participants with an odd last digit will be assigned to one study group, while participants with an even last digit will be assigned to the other study group. The intended probability of assignment to either study group is 50-50.

Which study group aligns with even/odd numbers varies randomly by cohort (e.g., odd numbers may be assigned to the on-demand format in one cohort but to the in-person format in the next cohort). Cohorts are formed around the length of time it takes to complete the program on a rolling basis based on demand. Evaluation staff use a random number generator in Excel to randomly vary what even or odd last digits mean for each upcoming cohort. The Excel spreadsheet with the results of the random number generator is shared with the RIDGE data manager via a secure Dropbox link. The data manager then prepares a sealed envelope with the random assignment information needed for each cohort's orientation, to be opened by the facilitator at the end of the orientation sessions when consent has been obtained. The facilitator then informs participants which group they have been assigned to based on the last digit of their inmate number. Once participants have been informed of their group assignment, they are considered part of the RCT study sample. The data manager enters study group assignments into the nFORM system. This process repeats with each new cohort in the RCT.

2. Data collection

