Wave 3 of data collection, which includes the local evaluation 6-month post-enrollment follow-up survey, is intended to be collected six months after program enrollment, with data collection efforts focused on five to seven months after program enrollment. However, the timing of the follow-up survey data collection can vary, with some participants taking the survey later than expected (e.g., an email with a survey link is opened and completed months after it was delivered) or earlier than expected (in the case of Franklin CBCF participants who complete their follow-up survey immediately upon release; see below). The tracking process typically begins at least 60 days prior to when a participant is due for a follow-up survey. This allows time for new contact attempts when email addresses are undeliverable and mailings are returned to the sender. The incarcerated population also tends to be a difficult population to get in touch with for various reasons. Someone just released from prison may be focusing on housing and employment needs or their contact information is outdated since they were enrolled into the program.

Waves 1 and 2 of all surveys are administered on paper with participants in person, due to technology restrictions in the prison facilities. Paper surveys are entered onto nFORM and Qualtrics (for the local evaluation surveys) within 72 hours of completion by RIDGE staff who have been certified in protecting human research participants. Paper surveys are securely transported by program staff to the RIDGE offices where they are entered and kept in locked storage.

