To increase follow-up response rates and with the approval of OFA, alternative follow-up data collection procedures were developed by the RIDGE and evaluation teams for one service site that enrolls most of the impact study participants at about 78%, Franklin CBCF. Many impact study participants from the Franklin CBCF service site go on to participate in a Department of Labor initiative immediately following their release from prison. As part of this initiative, participants are bussed from the Franklin CBCF to an American Jobs Center. TYRO Couples RCT participants who are part of this initiative are invited to complete a paper follow-up survey on the Thursday prior to the bus taking participants to the American Jobs Center the following Monday morning. Eligible participants who completed the survey will be handed a physical \$50 gift card upon boarding the bus. This follows guidelines of prisons where no monetary incentives can be administered on the premises. To be eligible for the follow-up survey, participants must have a signed consent form on file and have taken either the nFORM entrance survey or the local evaluation baseline survey. Evaluation staff will coordinate with program staff to ensure only those who are eligible for the follow-up survey are offered it. Paper surveys will be sealed in an envelope where they are given to a team member certified in protecting human research participants to enter the surveys into Qualtrics. Paper surveys are to be kept in locked storage at RIDGE offices and will be stored for a minimum of three years before being destroyed in accordance with IRB guidelines. This process is set to begin in May 2024.

Table 5. Key features of the data collection

Study group	Data source	Timing of data collection	Mode of data collection	Party responsible for data collection	Start and end date of data collection
Intervention (on-demand)	Survey Wave 1 (nFORM baseline and local evaluation baseline surveys)	Immediately following informed consent and randomization during orientation (within 1-2 weeks of enrollment)	In-person paper survey	RIDGE Staff	April 11, 2023 – November 30, 2024
	Survey Wave 2 (nFORM exit and local evaluation post-surveys)	Six weeks after program enrollment	In-person paper survey	RIDGE Staff	May 23, 2023 (or February 2023 for pilot cohort) – January 11, 2025

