Analyses will be conducted using the R Studio statistical software package. The basic model for this impact evaluation will include a dummy variable for intervention group assignment, equal to 1 if a participant was randomly assigned to receive the curriculum on-demand via tablet, and a participant's score at baseline as the main predictors of each outcome measure at follow-up. To enhance the precision of the impact estimates, we plan to include several other covariates in our models. For all outcome analyses, we will control for participant age, gender, and race, as well as the timing of a participant's follow-up survey (number of days between program enrollment and follow-up survey completion). We will also consider including a facility indicator to denote which site the participant received services at. Additionally, we will include any demographic variables that were shown to be significantly different between study groups during baseline equivalency analysis. For the healthy relationship attitudes outcome, we also plan to include relationship status at baseline as a covariate. This will only be available if a participant reports being in a relationship at baseline and at follow-up.

Table 6. Covariates included in impact analyses

Covariate	Description of the covariate
Age	Age (in years) as of the baseline data collection, as reported on the ACS
Gender	Self-reported gender identification as of the baseline data collection, as reported on the ACS
Race	Self-reported racial identification as of the baseline data collection, as reported on the ACS

Covariate	Description of the covariate
Timing of follow-up survey	Number of days between program enrollment date and date of follow-up survey completion to control for variation in survey timing
Relationship status (relationship attitude and behavior outcomes only)	Relationship status (1 = in a committed relationship, 0 = not in a committed relationship) as of the baseline data collection, as reported on the ACS

4. Sensitivity analyses for primary research questions

We plan to conduct several sensitivity analyses to test the robustness of our results. First, and as mentioned earlier in the plan, we will conduct a sensitivity analysis to see if and how our outcome construct measures change if we use 70% as a threshold for non-missing items instead of 80% as a threshold.

[figure not shown]

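### Scheduled time to release, judged before assignment under the nine-month rule, is in no outcome model, baseline check or sensitivity analysis; adding it would be a cheap, modest gain in precision and robustness.

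*Combined protocol and SAP*

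**What the plan says.** **Eligibility (C.1, Participant eligibility criteria).** Individuals qualify "if they are incarcerated adults aged 18 years or older and within nine months of release from prison". Remaining time can therefore be anything from almost none to nine months.

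**Models (D.3, Modeling approach, and Table 6).** Besides the arm indicator and baseline score, "we will control for participant age, gender, and race, as well as the timing of a participant's follow-up survey". Table 6 defines the timing covariate as "Number of days between program enrollment date and date of follow-up survey completion to control for variation in survey timing". Site is left open: "We will also consider including a facility indicator to denote which site the participant received services at". The only other route into the model is that "we will include any demographic variables that were shown to be significantly different between study groups during baseline equivalency analysis". Relationship status is added for relationship outcomes only.

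**Baseline equivalence and sensitivity analyses (D.2 and D.4).** The baseline check covers demographic characteristics (gender, age and race/ethnicity are the examples given) and baseline outcomes. The sensitivity analyses vary the item-missingness threshold, impute missing items, and restrict to surveys taken at 5 to 7 months. None uses release timing.

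**Follow-up (C.2 and Table 5).** The standard route is an emailed or texted link, or a phone call, at about six months. A different route, set to begin in May 2024, applies at "one service site that enrolls most of the impact study participants at about 78%, Franklin CBCF". Participants there who join the jobs initiative are offered a paper survey on the Thursday before the Monday bus. Table 5 puts Franklin follow-up at three to six months.

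**The concern.** The primary outcomes are attitudes to employment and to one's finances. The sample items ask about having the skills for a decent job and feeling overwhelmed by money. Answers could plausibly differ between someone still in custody and someone who has been looking for work for months. C.2 notes, when explaining why people are hard to reach, that "Someone just released from prison may be focusing on housing and employment needs".

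Days since enrollment does not measure distance from release. On the standard route, two people answering on day 180 are the same to the model on timing, even if one was released five months ago and the other has three months to serve. At Franklin, a participant answering just before the bus and one answering by link after release can also share a day count.

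The plan has no step that would show an imbalance in release timing between the arms. Time to release is not among the named baseline characteristics, and only demographic variables can enter the model through the baseline check. At stake are some precision and the credibility of a complete-case analysis, if time to release is related both to response and to score.

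**Working it through.** **Inputs from the documents**
- Eligibility window 0 to 9 months (C.1).
- Franklin CBCF share about 78% (C.2), leaving about 22%.
- Target analytic sample 768, 384 per arm (C.1).
- Follow-up to July 22, 2024 (Figure A.3): 64 of 206 and 52 of 190, so 116/396 = 29.3%.

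**Assumptions, because the documents give no figure**
- Time to release is uniform over 0 to 9 months, or over 1.5 to 9 months.
- Custody versus community shifts the score by d = 0.3 to 0.8 SD.
- Two-sided 5% test, 80% power. The plan states no alpha, power or effect size behind 768, so that target cannot be reproduced from its own inputs. The point does not depend on it.

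**Step 1. Who could be in custody at month 6.** On the standard route the share is (9 − 6)/(9 − lower limit): 3/9 = 33%, or 3/7.5 = 40%. Most Franklin participants are set aside here, because a survey window of three to six months tied to release implies release by about month 6. Applied to the remaining 22%, the share p of the whole sample is 0.22 × 0.333 = 7.3% or 0.22 × 0.40 = 8.8%. That is about 56 to 68 of 768. Moving the survey between months 5 and 7 widens the range to about 5 to 12%.

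**Step 2. Variance explained.** With v = d²p(1 − p) and R² = v/(1 + v):
- p = 0.073, d = 0.3: v = 0.09 × 0.068 = 0.0061, R² = 0.6%.
- p = 0.088, d = 0.8: v = 0.64 × 0.080 = 0.051, R² = 4.9%.

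**Step 3. Effect on precision.** The standard error is multiplied by √(1 − R²).
- R² = 0.6%: 0.997, a cut of 0.3%.
- R² = 4.9%: 0.975, a cut of 2.5%.

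At 384 per arm the detectable difference is 2.80 × √(2/384) = 0.202 SD. It falls to 0.2016 SD at the low end and 0.197 SD at the high end.

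**Step 4. Size of a chance imbalance.** One standard error of the difference in custody share is √[p(1 − p)(1/n₁ + 1/n₂)]. Multiplied by d, it gives the shift in the arm estimate.
- 64 and 52 completers: share SE 0.049 to 0.053, shift 0.015 to 0.042 SD. The standard error of the arm difference is √(1/64 + 1/52) = 0.187 SD.
- 384 per arm: share SE 0.019 to 0.020, shift 0.006 to 0.016 SD. The standard error of the arm difference is √(2/384) = 0.072 SD.

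Each shift is compared with the standard error at its own sample size. In both cases it is a minor part of it (8 to 23%).

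**Step 5. Franklin.** For the bus group, survey day is roughly release day minus four, so days to survey already carries most of the release information within that group. It does not do so in a pooled model with one timing coefficient for bus, link and phone respondents together. The documents do not say what share of Franklin participants take the bus route.

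**The case against.** **Bias.** A reader might infer that leaving out a predictor of the outcome biases the comparison. It does not, in expectation, if assignment works as random. Chance imbalance is already reflected in the standard error. This stands, and it limits the claim to precision and robustness.

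**Reach.** It is tempting to say that time to release largely decides whether the six-month score is given in custody. The documents do not support that for most of the sample. For the Franklin jobs-initiative group, release sets when the survey occurs. The reasoning fits the standard route, mainly the 22% outside Franklin, so a custody share of one third must not be applied to everyone.

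**In-custody respondents may be few.** Standard follow-up is by link or phone, C.2 cites technology restrictions in the facilities (for Waves 1 and 2), and Figure A.3 lists incarceration as a reason for non-completion. Time to release may thus affect whether a score exists more than where it is given. A covariate only partly addresses nonresponse.

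**Availability.** The nine-month rule can be applied as yes or no, and no section says a release date is recorded. C.1 describes the inmate number as one "which can also be used to look up their incarceration status within the ODRC facilities", which is not a scheduled date as known at enrollment. Wave 1 began in 2023, so dates for earlier cohorts may take a records pull or be unrecoverable.

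**Size.** The 0.3 to 0.8 SD shift has no source in the documents, and the remark about newly released people concerns contact, not scores. The R² above is for custody status with no other covariates in the model; the gain from a scheduled date on top of baseline score, age and days to survey may be smaller.

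What remains is that the variable precedes assignment, is implied by the entry rule, is plausibly related to response and outcome, and is unused.

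**Conclusion.** A true omission and a worthwhile low-cost improvement, not a flaw that invalidates the primary comparison. On the assumptions stated (uniform release times, a custody effect of 0.3 to 0.8 SD, few Franklin participants in custody at month 6), R² is about 0.6 to 5% and the saving is about 0.3 to 2.5% of the standard error.

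The further benefit, which the documents do not allow to be sized, is a more defensible complete-case analysis. The 29% is an interim figure: follow-up collection runs to May 31, 2025, so 64 and 52 should not be read as the final sample.

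**What to change.** 1. Obtain the scheduled release date as known at enrollment, from the eligibility check or facility records.
2. Add months from enrollment to scheduled release to Table 6 and to the baseline-equivalence table, and include it in the primary models. If it cannot be recovered for earlier cohorts, make it a prespecified sensitivity model.
3. Do not adjust for actual release date or for custody status at survey, since both arise after assignment. Report custody status at survey by arm, descriptively.
4. For that report, reconcile C.2 on the Franklin survey: one paragraph places it immediately upon release, another on the Thursday before the Monday bus.

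The cost is SAP wording, one data field going forward, a records pull for earlier cohorts, and one or two degrees of freedom. Some scheduled dates will later change, which weakens the covariate as a predictor but leaves it a pre-assignment variable. The plan is dated August 22, 2024, and baseline collection runs to November 30, 2024, so the change can be prespecified before data collection ends.

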Consent or refusal can also be indicated through the local evaluation baseline survey. The first item on the evaluation baseline survey reads: "By answering this question and typing my name below, I am acknowledging that I have been presented information about this study and am providing my voluntary consent to participate in the study described. I also understand that I can quit participating at any time and can skip any questions in this survey that I do not wish to answer without consequence, and further, I understand that all my answers are confidential and will not be shared with anyone outside of the research team." This item assures that the study information has been presented to participants and they know their rights as human subjects in a research study. Should someone decide that they no longer want to participate in the study, they can indicate on the local evaluation baseline survey and refuse to participate any further in the evaluation.

Random Assignment Process

After informed consent has been obtained, random assignment occurs. Random assignment takes place after one or two in-person orientation sessions, giving participants time to complete enrollment paperwork, provide consent, and take baseline surveys. During the one or two-in person orientation sessions, no curriculum content is covered until participants begin either the in-person or on-demand delivery format. Participants are randomized into the in-person or on-demand delivery format prior to the class starting, typically in one to two weeks. The participants attend classes one and two and are told at the beginning of class two whether they will be taking the course in person or via tablet.

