All outcome measures for this study are constructed averages calculated using a number of theoretically and empirically related survey items. As mentioned in the previous section, a respondent who answers some but not all survey items in a given outcome construct will have their outcome value assigned as missing if they do not respond to at least 80% of the items in the construct. We will not impute missing baseline or outcome data for our analyses. Based on the recommendation from ACF, we will use the cautious attrition threshold from the What Works Clearinghouse (WWC) to assess whether attrition can be considered high or low.

Assessment of baseline equivalence

Per the WWC's standards, we will use effect sizes (i.e., standardized mean differences), to examine the baseline equivalence between the study groups. Effect size is defined as the difference between the intervention group mean and the comparison group mean, divided by the pooled standard deviation. We will calculate the effect size for demographic characteristics (such as gender, age, and race/ethnicity, as reported on the nFORM Applicant Characteristics Survey) and each baseline outcome of interest depending on the type of variable: Hedge's g , for continuous variables; and Cox's index, for dichotomous variables. We can determine baseline equivalence by comparing each outcome's effect size using the WWC standard, which suggests that if the corresponding effect size is 0.05 or less in absolute value, it is considered "small," and we can conclude that it satisfies baseline equivalence without statistical adjustment. However, if the effect size falls between 0.05 and 0.25, it is considered "moderate," and it will require a statistical adjustment to meet baseline equivalence (we will use statistical adjustments such as regression adjustments or matching/weighting). Lastly, in the case that the effect size is greater than 0.25, it will be considered "large", which shows that the differences at baseline are too large to meet WWC standards, even with statistical adjustments. In that case, we will apply appropriate caveats to any interpretation of the results.

Condition crossover

At the primary RCT enrollment site, Franklin CBCF, condition crossover is not possible due to restrictions put in place when designing the implementation of the two delivery formats. If a participant who was

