assigned to the on-demand group attempts to attend the in-person classes, the facilitators will not allow them to sit in on in-person classes and will remind them that they are to complete the curriculum via tablet in the designated classroom. Tablets must be checked out to be used in the designated space, and a program staff member will be present to verify that participants who attempt to check out a tablet have been assigned to the on-demand group.

Other facilities participating in the RCT may not have the same restrictions in place to prevent condition crossover. In all participating facilities, facilitators have been trained on the design of the study and understand the importance of enforcing adherence to the condition to which a participant has been assigned. The evaluation team has a record of which study group each participant should have been assigned to based on the last digit of the inmate number and the randomization schema for each cohort, so cross-over to a different treatment condition can be flagged, and the prevalence of condition crossover will be disclosed in the final report.

3. Analytic approach

Modeling approach

Due to the nature of the continuous dependent variables of interest, we plan to fit a model using linear regression for all primary and secondary analyses for this study. We will model curvatures to ensure that the model is still linear in the parameters by doing re-expressions of the independent variables to fit a curve. We will also check the adequacy of the model to meet the remaining assumptions of a linear model (normality, multicollinearity, homoscedasticity, and independence) by reviewing the diagnostic plots and transforming our variables accordingly, if necessary. However, based on the nature of the survey data we will be using, we do not anticipate needing to fit a nonlinear model.

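### On-demand participants who switch to in-person services are removed from the study after randomisation, which can bias the as-randomised comparison by an unknown amount in either direction

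*Combined protocol and SAP*

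**What the plan says.** The rule is in section C.1, under Participant eligibility criteria. Its trigger is worded as "In instances where unexpected situations arise, such as technological issues with the tablets". In that case "participants can opt out of the treatment group and receive in person services if it is more convenient or preferable to them". The consequence follows at once: "This would remove the participant from the study, but still allow the participant to continue with the TYRO curriculum". Section A.1 defines the treatment group as the on-demand arm.

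The Random Assignment Process text in C.1 fixes when a person joins the trial: "Once participants have been informed of their group assignment, they are considered part of the RCT study sample".

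Section D.2, Condition crossover, says: "At the primary RCT enrollment site, Franklin CBCF, condition crossover is not possible due to restrictions put in place". It adds that if an on-demand participant "attempts to attend the in-person classes, the facilitators will not allow them to sit in on in-person classes". Section C.2 describes this as the site that "enrolls most of the impact study participants at about 78%, Franklin CBCF". For the other facilities, D.2 says only that the same restrictions may be lacking, that crossover can be flagged against the assigned group, and that its prevalence will be reported.

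Section D.3 codes the treatment variable by random assignment. Section D.1 limits the analysis to complete cases. Section D.4 plans three sensitivity analyses: a 70% item threshold, item mean imputation, and restriction to the intended follow-up window. Section D.2 applies the cautious What Works Clearinghouse (WWC) attrition threshold without saying whether people who opt out count as attrition.

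**The concern.** Nobody can opt out of a group before being told of it, so the removal comes after the person has joined the RCT sample. It depends partly on what the person finds convenient or preferable once the assigned format has run into difficulty. It also acts on one arm: the only exclusion tied to the in-person format, for people with conflicting commitments, is applied before random assignment and so falls on both arms alike.

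The on-demand arm that remains may therefore be a selected subset, compared with an in-person arm that has had no such selection by this route. If those who leave would have scored worse, the result favours on-demand; if better, it favours in-person. If the cause has nothing to do with the person, such as a random tablet fault, there is no bias. The plan gives no way to tell which applies.

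A second effect is conditional. If removed people also leave the attrition denominator, attrition in the on-demand arm is understated, and with it the overall and differential figures used for the WWC check. Figure A.3 bases follow-up eligibility only on consent and a baseline survey, so it is unclear whether removed people are still surveyed and counted.

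**Working it through.** **Is the exclusion repaired elsewhere?**

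- The assignment indicator in D.3 gives an as-assigned contrast, but only among people still in the data set.
- The crossover text in D.2 flags and reports switches. It gives no analysis rule.
- Baseline equivalence checks and covariates deal with measured differences only.
- None of the three sensitivity analyses in D.4 concerns removal.

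**Inputs from the plan.** Target analytic sample 768, 384 per arm (C.1). Franklin CBCF share about 78% (C.2), so other sites about 22%. Interim follow-up 64/206 = 31.1% and 52/190 = 27.4%; dropped out 7/206 = 3.4% and 4/190 = 2.1% (Figure A.3; the text available does not label the arms).

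**Assumptions, not in the plan.** p = share of the on-demand arm removed; d = stayer-minus-leaver difference in SD units remaining after covariate adjustment; two-sided 5% test; no precision gain from covariates. The plan states no alpha, power or effect size, so 768 cannot be reproduced and serves only as the scale.

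**Bias.** With stayers' mean S and leavers' mean L, the whole on-demand arm has mean (1 − p)S + pL. After removal the trial observes S. Bias = S − [(1 − p)S + pL] = p(S − L) = p × d, with the sign of d.

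**Type I error.** SE = sqrt(4/768) = 0.0722 SD. Type I error = P(|Z + bias/SE| > 1.96), the same for either sign of d.

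| Scenario | p | \|d\| | Bias (SD) | Type I error |
|---|---|---|---|---|
| (a) Opt-out possible at all sites | 5% | 0.3 | 0.015 | 5.5% |
| | 10% | 0.5 | 0.050 | 10.7% |
| | 20% | 0.5 | 0.100 | 28.3% |
| (b) Outside Franklin CBCF only (p × 0.22) | 1.1% | 0.3 | 0.003 | 5.0% |
| | 2.2% | 0.5 | 0.011 | 5.3% |
| | 4.4% | 0.5 | 0.022 | 6.1% |
| (c) p set to interim dropped-out share | 2.1% | 0.3 | 0.006 | 5.1% |
| | 3.4% | 0.5 | 0.017 | 5.6% |
| (d) Leavers do not differ | any | 0 | 0 | 5.0% |

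The 20% row is the extreme corner. Shrinking the on-demand arm to 384(1 − p), instead of holding the analysed total at 768, changes 10.7% to 10.4% and 28.3% to 25.7%. The dropped-out counts in (c) are not identified as opt-outs, and removed people may not be counted there.

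For scale, 384 per arm detects 2.80 × sqrt(2/384) = 0.202 SD with 80% power (assumed). A bias of 0.05 SD is about a quarter of that.

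**Attrition**, only if removed people leave the denominator and are not surveyed. With follow-up rate r among those who stay, true attrition is 1 − r(1 − p) and reported attrition is 1 − r. The understatement is p × r:

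- Scenario (a): 0.05 × 0.274 = 1.4 to 0.20 × 0.311 = 6.2 percentage points.
- Scenario (b): 0.011 × 0.274 = 0.3 to 0.044 × 0.311 = 1.4 percentage points.

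**The case against.** The plan is otherwise written on an as-assigned basis. C.1 and D.3 define the comparison by random assignment, and D.2 already promises to check crossover against assignment and disclose it. On this view a single sentence is out of line. That is fair, but that sentence states a rule, and coding by assignment cannot bring back people already removed.

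The effect may be small. The trigger is limited to unexpected situations, and if D.2 is right that crossover cannot happen at the site with about 78% of participants, scenario (b) applies. The 28% figure needs 20% removed, a residual difference of 0.5 SD and the full 768. With only the interim completers (64 and 52), SE = sqrt(1/64 + 1/52) = 0.187 and the same corner gives about 8%. All this stands as a limit on size. A smaller sample reduces the type I inflation but leaves the bias unchanged.

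The two Franklin CBCF statements might also coexist, one barring casual attendance and the other allowing a sanctioned exit. If so, D.2 no longer bounds p and scenario (b) loses its basis.

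The denominator point is conditional. Figure A.3 lists drop-outs under the eligible boxes, which suggests that leavers stay in the count, and the upper part of the diagram could not be seen.

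Finally, opting out might be treated as ordinary withdrawal. The baseline consent item covers that separately, for both arms: "I also understand that I can quit participating at any time". Changing format is not the same as refusing surveys.

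Interim non-response is probably the larger threat: 116 of 396 eligible people (29.3%) had completed follow-up, though some may still have been in their window.

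**Conclusion.** The concern holds. The plan prescribes removal after randomisation, in one arm, partly on preference, and provides neither an analysis that keeps these people nor a sensitivity analysis for their loss. Confidence is high that the rule exists and can bias the result. The size and direction cannot be settled from the plan.

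Under the assumed values, the bias runs from zero through 0.003–0.022 SD (switching only outside Franklin CBCF) to 0.015–0.10 SD (switching possible everywhere, with 5–20% removed and differences of 0.3–0.5 SD). This should be fixed because it is avoidable and cheap to correct; a large effect has not been shown.

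**What to change.** - Replace the removal sentence in C.1. Participants who change format stay in the RCT sample, are surveyed at Waves 2 and 3 on the same schedule unless they withdraw consent, and are analysed in the group to which they were randomised.
- Report switches by arm and site as crossover.
- Compute overall and differential WWC attrition over everyone randomised, including those already removed.
- Follow up opt-outs already removed who are still in their window, where consent allows.
- Present any analysis that excludes switchers only as a sensitivity analysis.
- Reconcile the opt-out text in C.1 with the Franklin CBCF statements in D.2, so that the plan says whether opt-out can occur there.

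The option to change format is untouched.

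**Cost.** Revised wording, probably an IRB amendment (C.1 shows that earlier study and data-collection revisions went that way), and existing surveys with the $50 follow-up incentive for the people retained. That is about 4 to 17 people in scenario (b) (0.011 and 0.044 × 384) and 19 to 77 in scenario (a) (0.05 and 0.20 × 384). Table 5 has baseline collection running to November 30, 2024 and follow-up to May 31, 2025, so the change was still workable at the plan's date of August 22, 2024. The statistical downside is slight dilution of the as-randomised estimate by switchers.
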